5.5.1.9 Grade ≥ 3 congestive heart failure will be considered a DLT and

THIS PROTOCOL IS FOR RESEARCH PURPOSES ONLY, SEE PAGE 1 FOR USAGE POLICY

require removal from protocol therapy.

5.5.1.10 Any toxicity that is possibly related to the study medication that requires removal from protocol therapy. Note: Allergic reactions that necessitate discontinuation of study drug will not be considered a dose-limiting toxicity.

5.5.2 Hematological dose limiting toxicity

5.5.2.1 In patients evaluable for hematological toxicity (see [Section 4.1.7.1](#)), hematological dose limiting toxicity is defined as:

- Grade 4 neutropenia for > 7 days
- Platelet count < 20,000/mm³ on 2 separate days, or requiring a platelet transfusion on 2 separate days, within a 7 day period
- Myelosuppression that causes a delay of > 14 days between treatment cycles.

5.5.2.2 Other hematological dose-limiting toxicities:

- Any arterial thromboembolic event (including cerebrovascular ischemia, peripheral or visceral arterial ischemia)
- Any \geq Grade 3 venous thromboembolic event
- Any thrombotic event requiring systemic anti-coagulation
- Any \geq Grade 3 hemorrhage

5.5.2.3 Note: Grade 3 or 4 febrile neutropenia will not be considered a dose-limiting toxicity.

6.0 DOSE MODIFICATIONS FOR ADVERSE EVENTS

The Study Chair must be notified of any dosage modification or use of myeloid growth factor.

6.1 Dose Modifications for Hematological Toxicity

- 6.1.1 Patients who have dose-limiting thrombocytopenia will have their treatment held. Counts should be checked every 3-4 days for thrombocytopenia during this time. If the toxicity resolves to meet eligibility criteria parameters within 14 days, the patient may resume subsequent infusions at the next lower dose level. Doses reduced for toxicity will not be re-escalated, even if there is minimal or no toxicity with the reduced dose.
- 6.1.2 Patients who have dose-limiting neutropenia will have their treatment held. Counts should be checked every other day for neutropenia during this time. If the toxicity resolves to meet eligibility criteria parameters within 14 days, the patient may resume subsequent infusions at the next lower dose level. Doses reduced for toxicity will not be re-escalated, even if there is minimal or no toxicity with the reduced dose.
- 6.1.3 Patients who experience dose-limiting thrombocytopenia or neutropenia after two dose reductions must be removed from protocol therapy.
- 6.1.4 If, within a cycle, a dose-limiting hematological toxicity does not resolve to meet eligibility criteria within 14 days as stipulated in Sections 6.1.1 and 6.1.2 above, the patient must be removed from protocol therapy. In addition, patients who have a dose-limiting hematological toxicity that does not resolve to eligibility criteria within 21 days after the planned start of the *next* treatment cycle must be removed from protocol therapy.
- 6.1.5 Patients who experience any of the following events must be removed from protocol therapy:
 - Any arterial thromboembolic event (including cerebrovascular ischemia, peripheral or visceral arterial ischemia)
 - Any \geq Grade 3 venous thromboembolic event
 - Any thrombotic event requiring systemic anti-coagulation
 - Any \geq Grade 3 hemorrhage

6.2 Dose Modifications for Non-Hematological Toxicity

- 6.2.1 Patients who have any dose-limiting non-hematological toxicity (as defined in [Section 5.5.1](#)) may continue on protocol therapy upon meeting eligibility lab requirements or baseline but should receive subsequent infusions at the next lower dose level, except as outlined in Sections [6.4](#) and [6.5](#). Doses reduced for toxicity will not be re-escalated, even if there is minimal or no toxicity with the reduced dose.

THIS PROTOCOL IS FOR RESEARCH PURPOSES ONLY, SEE PAGE 1 FOR USAGE POLICY

6.2.2 If the same non-hematological dose-limiting toxicity recurs after one dose reduction, the patient must be removed from protocol therapy.

6.2.3 Patients who have a dose-limiting non-hematological toxicity that does not resolve to baseline or eligibility criteria within 21 days after the planned start of the next treatment cycle must be removed from protocol therapy.

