5.5.1.2 Dose-limiting hypertension

- Any Grade 4 hypertension
- A blood pressure > 25 mmHg above the 95th percentile for age, height, and gender ([Appendix VIII](#)) confirmed by repeated measurement is dose limiting.
- In patients who begin antihypertensive therapy a blood pressure > 10 mmHg but ≤ 25 mmHg above the 95th percentile for age, height, and gender ([Appendix VIII](#)) for > 14 days is dose limiting.

5.5.1.3 Non-hematological toxicity that causes a delay of ≥ 14 days between treatment cycles will be considered dose-limiting.

5.5.1.4 Proteinuria: Urine protein/creatinine (P/C) ratio > 1 and < 1.9 confirmed with a second measurement within 72 hours will be considered a DLT (See [Section 6.5](#))

5.5.1.5 Any gastrointestinal perforation event will be considered a DLT and require removal from protocol therapy.

5.5.1.6 Grade ≥ 2 wound complication or wound dehiscence will be considered a DLT and require removal from protocol therapy.

5.5.1.7 Grade ≥ 3 hepatic failure will be considered a DLT and require removal from protocol therapy.

5.5.1.8 Grade ≥ 2 reversible posterior leukoencephalopathy syndrome (RPLS) will be considered a DLT and require removal from protocol therapy.

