10.0 CRITERIA FOR REMOVAL FROM PROTOCOL THERAPY AND OFF STUDY CRITERIA

10.1 Criteria for Removal from Protocol Therapy

- a) Clinical (including physical examination or serum tumor markers) or radiographic evidence of progressive disease (See [Section 12.0](#)).
- b) Adverse Events requiring removal from protocol therapy (See [Section 6.0](#)).
- c) Refusal of protocol therapy by patient/parent/guardian
- d) Non-compliance that in the opinion of the investigator does not allow for ongoing participation.
- e) Completion of 8 cycles of therapy.
- f) Physician determines it is not in the patient's best interest.
- g) Repeated eligibility laboratory studies (CBC with differential, bilirubin, ALT (SGPT) or serum creatinine) are outside the parameters required for eligibility prior to the start of ramucirumab (See [Section 8.1](#)).
- h) Study is terminated by Sponsor.
- i) Pregnancy

Patients who are removed from protocol therapy during cycle 1 should continue to have the required observations in [Section 8.1](#) until the originally planned end of the cycle or until all adverse events have resolved per [Section 13.4.4](#), whichever happens LATER. The only exception is with documentation of the patient's withdrawal of consent. Patients who are removed from protocol therapy in subsequent cycles should have the necessary observations to ensure adequate clinical care.

Patients who are off protocol therapy are to be followed until they meet the criteria for Off Study (see below). Ongoing adverse events, or adverse events that emerge after the patient is removed from protocol therapy, but within 30 days of the last dose of investigational agent, must be followed and reported via RAVE and CTEP-AERS (if applicable). Follow-up data will be required unless consent is withdrawn.

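### Protocol 6.2.1 permits continued dosing, one level lower, after any non-hematological DLT, while 5.5.1.5 to 5.5.1.9 require removal for five of those DLTs

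*Protocol*

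**What the plan says.** Protocol Section 6.2.1 governs every non-hematological DLT that Section 5.5.1 defines. Such a patient "may continue on protocol therapy upon meeting eligibility lab requirements or baseline but should receive subsequent infusions at the next lower dose level". The only exceptions named are Sections 6.4 (hypertension) and 6.5 (proteinuria).

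Five items of Section 5.5.1 say something else. Item 5.5.1.5 reads: "Any gastrointestinal perforation event will be considered a DLT and require removal from protocol therapy". Item 5.5.1.6 says that a Grade 2 or higher "wound complication or wound dehiscence will be considered a DLT and require removal from protocol therapy". Items 5.5.1.7 (hepatic failure, Grade 3 or higher), 5.5.1.8 (RPLS, Grade 2 or higher) and 5.5.1.9 (congestive heart failure, Grade 3 or higher) carry the same removal requirement.

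Section 10.1(b) makes "Adverse Events requiring removal from protocol therapy" a reason to stop protocol therapy and refers the reader to Section 6.0. It does not cite Section 5.5.

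**The concern.** The two sections do not give the same instruction for the same five events. A site that looks up management in Section 6, which is where 10.1(b) sends it, finds a rule that permits further infusions at a reduced dose. A site that works from Section 5.5.1 finds that the patient must come off therapy.

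The question is not confined to Cycle 1. Section 5.5 makes the first cycle the DLT observation period for dose escalation, but 6.2.1 has no such limit and treatment can run to 8 cycles. For an event in a later cycle, Section 6 is the natural place to look. The rule can also be carried out in practice: the RP2D is dose level 2, and Section 5.3.1 lists a level below it.

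At stake are the safety of a patient who has had one of these events, and the consistency of what sites record. The SAP lists reasons for treatment discontinuation (6.2), counts dose adjustments (6.7.1) and summarizes separately the adverse events leading to discontinuation and to dose modification (6.7.3). The same event could fall under either heading, depending on which section the site followed.

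**Working it through.** No arithmetic applies, because the point depends on no rate, error level or sample size. The check sets the rules side by side and then looks for a clause that settles the difference.

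**Step 1: the five events under each rule.**

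| Item | Event | Section 5.5.1 | Section 6.2.1 | Excepted from 6.2.1? |
|---|---|---|---|---|
| 5.5.1.5 | Gastrointestinal perforation, any | Removal | May continue, one level lower | No |
| 5.5.1.6 | Wound complication or dehiscence, Grade ≥ 2 | Removal | May continue, one level lower | No |
| 5.5.1.7 | Hepatic failure, Grade ≥ 3 | Removal | May continue, one level lower | No |
| 5.5.1.8 | RPLS, Grade ≥ 2 | Removal | May continue, one level lower | No |
| 5.5.1.9 | Congestive heart failure, Grade ≥ 3 | Removal | May continue, one level lower | No |

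Five items carry an explicit removal requirement and fall within 6.2.1. Its exceptions cover 0 of the 5.

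**Step 2: does another clause settle it?**

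- 6.2.2 removes a patient only if the same DLT comes back after one dose reduction. A first event is not caught.
- 6.2.3 removes a patient only if the DLT has not resolved within 21 days after the planned start of the next cycle. An event that resolves in time is not caught.
- 5.2 allows a new cycle on at least stable disease and eligibility laboratory values. It names none of the five events, and laboratory values need not reflect a past perforation or wound dehiscence.
- 6.3, 6.4 and 6.5 deal with infusion reactions, hypertension and proteinuria. They state their own removal rules and mention none of the five.
- 10.1(b) points to Section 6.0, where none of the five is listed.
- The experimental design schema says that therapy stops for a drug-related DLT requiring removal, but does not say which DLTs those are.

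No clause says whether 5.5.1 or 6.2.1 governs when they differ.

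**Step 3: does the dose-finding result depend on it?** Each of the five is a DLT under either rule if attributable to protocol therapy. Under 11.2.1 and 11.6.2, a treated patient with a Cycle 1 DLT is evaluable whether or not dosing continues. The rolling-six decisions, and so the MTD, use only the Cycle 1 DLT count. Sections 5.1 and 5.3.1 also record that escalation is complete and that the RP2D has been set at 12 mg/kg. The DLT count and the MTD/RP2D are therefore unaffected.

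**The case against.** The strongest reply is that the wording of 5.5.1 prevails in practice. Section 6.2.1 is permissive, whereas the five items are mandatory and event-specific, so a site that removes the patient breaches neither section. Section 6.2.1 also sends the reader to 5.5.1 to establish that the event is a DLT, and the sentence that makes it one also requires removal. The reference in 10.1(b) to Section 6.0 is not worded as a limit. There is oversight as well: DLTs go to the Study Chair within 24 hours (5.4), the Study Chair must be told of any dose modification (6.0), and study leadership reviews DLT evaluations weekly (14.4.2).

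Much of this stands. A site that reads 5.5.1 would probably remove the patient, and the oversight lowers the chance of re-dosing. But no order of precedence is written down, 6.2.1 has its own exception list that omits these items, and oversight does not say which text governs.

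Three stronger readings are tempting, and the documents do not support them:

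- A reader might count 5.5.1.10 as a sixth conflicting item. It lists "Any toxicity that is possibly related to the study medication that requires removal from protocol therapy", which classes as a DLT something that already has to lead to removal. It names no event and orders no removal itself.
- A reader might see in 6.1.5, which begins "Patients who experience any of the following events must be removed from protocol therapy", a practice of restating removal rules that 6.2 fails to follow. But 5.5.2.2 lists the thrombotic and hemorrhagic events only as DLTs, without mentioning removal, so 6.1.5 restates no removal rule from there.
- A reader might measure the exposure as 24 infusions (8 cycles × 3). That is the whole planned course, not dosing after one of these events.

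**Conclusion.** The inconsistency is real and narrow. For five named DLTs, 5.5.1 requires removal while 6.2.1, by its letter, permits continued dosing one level lower. None of the five is covered by the exceptions in 6.2.1, and 10.1(b) directs sites to the section where the removal requirement is absent. These are not two opposing commands, since one rule is permissive. The defect is that a written rule allows what another written rule forbids.

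A reader might infer that the MTD or RP2D is in doubt. It is not, because each event counts as a DLT under both rules. The consequences are for the safety of individual patients and for the descriptive counts of dose reduction against discontinuation. How often this would arise cannot be estimated from the documents.

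The conclusion rests on reading 6.2.1 literally and on the absence of any precedence clause in the text available. It takes no position on which clinical action should apply. It is an internal inconsistency, not a disputable design choice, and because it bears on re-dosing after serious events it should be corrected.

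**What to change.** Reconcile Sections 5.5.1.5 to 5.5.1.9, 6.2.1 and 10.1(b) so that all give the same action for the five events. The sponsor decides which action stands. If it is the one in 5.5.1, add the five items to the exception clause of 6.2.1 and list them in Section 6.2. If it is the one in 6.2.1, amend the five items in 5.5.1. In either case, make 10.1(b) cite every section that contains a removal requirement.

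The cost is a few words at the next amendment, with no added patients, visits or procedures.

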6.3 Dose Modifications for Infusion-Related Reactions

For patients who have allergic or acute infusion reactions to ramucirumab, therapy modifications based on grade should be as follows.

[figure not shown]
Grade Infusion Related Reaction	Action
Grade 1 Transient flushing or rash, drug fever $< 38^{\circ}\text{C}$	
Monitor patient until recovery from symptoms; infusion rate may be slowed.If the infusion is interrupted, then restart the infusion at 50% of the original infusion rate when symptoms resolve. Monitor patient closely. 
The following prophylactic premedications are recommended: diphenhydramine 1 mg/kg with max 50 mg (or equivalent) and/or acetaminophen 10-15 mg/kg (max 1000 mg) at least 30 minutes before additional ramucirumab administrations, slowing infusion rate as above.

Grade 2 Rash, flushing, urticaria, dyspnea, drug fever $\geq 38^{\circ}\text{C}$	
Stop infusion, begin an IV infusion of normal saline, and treat the subject with diphenhydramine 1 mg/kg with max 50 mg IV (or equivalent) and/or acetaminophen 10-15 mg/kg (max 1000 mg); remain at bedside and monitor patient until resolution of symptoms. Corticosteroid or bronchodilator therapy may also be administered as appropriate.If the infusion is interrupted, then restart the infusion at 50% of the original infusion rate when symptoms resolve. Monitor patient closely.If symptoms recur, then no further ramucirumab will be administered at that visit. Administer diphenhydramine 1 mg/kg with max 50 mg IV (or equivalent), and remain at bedside and monitor the patient until resolution of symptoms. 
The following prophylactic premedications are recommended: diphenhydramine 1 mg/kg with max 50 mg IV (or equivalent) and acetaminophen (10-15 mg/kg, max 1000 mg) should be administered at least 30 minutes before additional ramucirumab administrations. If clinically indicated, corticosteroids (recommended dose: 1-2 mg/kg/day methylprednisolone IV or equivalent) may be used.

Grade 3 or 4 Symptomatic bronchospasm with	
Immediately discontinue infusion of ramucirumab.Begin an IV infusion of normal saline, and treat the subject as follows. Recommend bronchodilators, epinephrine 0.2 to

or without urticaria, allergy related edema/angioedema, hypotension; Anaphylaxis	
1 mg of a 1:1,000 solution for subcutaneous administration, 0.1 to 0.25 mg of a 1:10,000 solution injected slowly for IV administration, 0.01 mg/kg of 1:1000 dilution (0.01 ml/kg/dose) for intramuscular administration, and/or diphenhydramine 1 mg/kg with max 50 mg IV with 1-2 mg/kg/day methylprednisolone IV (or equivalent), as needed.
 
• Patient should be monitored until the investigator is comfortable that the symptoms will not recur.• Ramucirumab will be permanently discontinued. 
Investigators should follow their institutional guidelines for the treatment of anaphylaxis. Remain at bedside and monitor patient until recovery from symptoms. In the case of late-occurring hypersensitivity symptoms (e.g., appearance of a localized or generalized pruritis within 1 week after treatment), symptomatic treatment may be given (e.g., oral antihistamine, or corticosteroids).

--	---

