5.3 Dose Escalation Schema (Completed)

5.3.1 Inter-Patient Escalation for Part A:

Part A of the study is an open-label, Phase 1, dose-escalation study. Ramucirumab will be administered as an intravenous infusion over 60 minutes every other week for 3 infusions over a 6-week period constituting a cycle. The anticipated maximum number of evaluable subjects required to complete Part A is 24 patients (See [Section 11.1](#)).

Patients should receive diphenhydramine (1 mg/kg, maximum dose 50 mg) (or alternative antihistamine) within 30 to 60 minutes prior to each infusion with ramucirumab. Anaphylactic precautions should be observed during ramucirumab administration. If \geq Grade 2 infusional reaction occurs, the infusion should be stopped and supportive care given as per institutional guidelines.

See [Section 6.3](#) for management and dose modification guidelines for infusional reactions (IRR). For the first infusion, vital signs should be monitored prior to infusion, every 30 (\pm 5) minutes during the infusion, and every 30 (\pm 5) minutes for a one-hour observation period after the completion of the infusion. If there is no evidence of an IRR during the initial 2 infusions of ramucirumab, then no observation period is required for subsequent treatment cycles. In the event an IRR occurs thereafter, then the one-hour observation period should be reinstated.

The starting dose of ramucirumab will be 8 mg/kg (dose level 1) with dose levels for subsequent groups of patients as follows.

Dose Level	Dose (mg/kg)
------------	--------------

THIS PROTOCOL IS FOR RESEARCH PURPOSES ONLY, SEE PAGE 1 FOR USAGE POLICY

-1	6
1*	8
2	12
3^	≤ 16

* Starting Dose Level

^ Escalation to Dose level 3 will only be considered after evaluation of PK and toxicity at dose Level 2. If $C_{min,ss}$ of $\geq 50 \mu\text{g/mL}$ has not been achieved in at least 5 out of 6 evaluable patients from dose level 2, and if the MTD has not yet been reached, then dose level 3 will be considered.

Ramucirumab will be provided by Eli Lilly and Company. Do not use commercial supply.

There will be no escalations beyond dose level 3 (16 mg/kg). If the MTD has been exceeded at the first dose level, then the subsequent cohort of patients will be treated at a dose of 6 mg/kg (dose level -1). If dose level -1 is not well tolerated, further de-escalation will not occur. The study will be closed to accrual.

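### The Grade 3 or 4 infusion-reaction row prints a fixed 0.2 to 1 mg subcutaneous epinephrine option with no weight limit; below 20 kg all of that range exceeds the row's own 0.01 mg/kg intramuscular amount

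*Protocol*

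**What the plan says.** Protocol section 6.3 has a table of actions by grade of infusion reaction. For Grade 3 or 4 the infusion is stopped for good and a list of treatments follows. The epinephrine entry runs across a page break. It starts "Recommend bronchodilators, epinephrine 0.2 to" and continues "1 mg of a 1:1,000 solution for subcutaneous administration". Two other epinephrine options follow: "0.1 to 0.25 mg of a 1:10,000 solution injected slowly for IV administration" and "0.01 mg/kg of 1:1000 dilution (0.01 ml/kg/dose) for intramuscular administration".

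The list is joined by and/or, and it closes with diphenhydramine given with "1-2 mg/kg/day methylprednisolone IV (or equivalent), as needed". Every item is therefore optional. The row later adds: "Investigators should follow their institutional guidelines for the treatment of anaphylaxis". For reactions of Grade 2 or higher, section 5.3.1 says "the infusion should be stopped and supportive care given as per institutional guidelines", and then refers the reader to section 6.3 for management.

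Of the three epinephrine options, only the intramuscular one is scaled to weight. Neither fixed range carries a weight or age limit.

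**The concern.** This is a paediatric trial, and its entry rules admit very small children. Apart from epinephrine, every drug given a dose in the 6.3 table (diphenhydramine, acetaminophen, methylprednisolone) is dosed per kilogram, and the first two also carry maxima. The premedication in section 5.3.1 follows the same pattern: "Patients should receive diphenhydramine (1 mg/kg, maximum dose 50 mg". The fixed subcutaneous range departs from that convention, and it stands beside a weight-scaled dose of the same solution.

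The row would be consulted in an emergency, when there is little time to reconcile two entries. A clinician who followed the fixed range in a small child could give more than the row's own weight-based amount, and at the upper end several times more. The stake is the safety of an individual patient. No trial conclusion depends on it.

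**Working it through.** **Inputs**

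- Fixed subcutaneous range: 0.2 to 1 mg of 1:1,000 (section 6.3, Grade 3 or 4 row).
- Weight-based intramuscular dose: 0.01 mg/kg of 1:1000, also printed as 0.01 mL/kg (same row).
- Fixed intravenous range: 0.1 to 0.25 mg of 1:10,000 (same row).
- Population: age from 12 months (4.1.1); a creatinine limit for children aged 1 to under 2 years (4.1.7.2); no minimum weight among the eligibility criteria; preparation volumes for 8-25 kg and for under 8 kg (9.1.5).

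**Step 1: the plan's own figure.** A 1:1,000 solution is 1 g in 1,000 mL, or 1 mg/mL. Then 0.01 mg/kg ÷ 1 mg/mL = 0.01 mL/kg, which matches the printed volume. The row's conversion is correct. The subcutaneous and intramuscular options use the same strength, so their milligram amounts can be compared directly.

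**Step 2: where the fixed range meets the weight-based amount.** Crossover weight = fixed dose ÷ 0.01 mg/kg.

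- Bottom of the range: 0.2 ÷ 0.01 = 20 kg.
- Top of the range: 1 ÷ 0.01 = 100 kg.

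Below 20 kg every value in the fixed range is larger than 0.01 mg/kg. Between 20 and 100 kg only part of the range is larger.

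**Step 3: the size of the gap.** For weight w, the weight-based amount is x = 0.01 × w, and the multiples are 0.2/x and 1/x.

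| Weight (kg) | 0.01 mg/kg (mg) | Bottom of range, multiple | Top of range, multiple |
|---|---|---|---|
| 8 | 0.08 | 2.5 | 12.5 |
| 10 | 0.10 | 2.0 | 10.0 |
| 15 | 0.15 | 1.33 | 6.67 |
| 20 | 0.20 | 1.0 | 5.0 |
| 40 | 0.40 | 0.5 | 2.5 |

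The right-hand column applies only if the top of the range is chosen. The row does not say where in the range to go for a small child.

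**Step 4: the intravenous range in the same cell.** It is unscaled too. Against the same 0.01 mg/kg, the crossovers are 0.1 ÷ 0.01 = 10 kg and 0.25 ÷ 0.01 = 25 kg, so the whole range exceeds that amount below 10 kg. At 8 kg the multiples are 0.1/0.08 = 1.25 and 0.25/0.08 = 3.1. Strength and route both differ here, so this shows only that the range is unscaled.

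**Step 5: reach.** The figure matters only for a Grade 3 or 4 reaction, in a patient under 20 kg, who is then given the subcutaneous option. The documents give no rate for any of these three conditions and no patient weights, so no number of affected patients can be calculated.

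**The case against.** The strongest reply is that the row largely protects itself. It defers to institutional anaphylaxis guidelines, section 5.3.1 does the same from Grade 2 upward, every item is optional, and a weight-based epinephrine dose is already printed. This stands as a reason for low priority. It does not remove the problem: neither sentence says that institutional guidelines override the printed doses, and neither limits the fixed range by weight or age.

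A second reply is that harm cannot be shown, because the comparison sets a subcutaneous dose against an intramuscular one. That stands in full. A reader might infer from the multiples that the protocol prescribes an overdose. The documents do not support that, since they contain no paediatric subcutaneous standard. The intramuscular dose is only the row's own reference for the same solution.

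A third reply concerns size. A reader might also infer that any small child given the fixed range would receive several times the weight-based amount. The table above does not bear that out: at 15 kg the bottom of the range is 1.33 times. The wording that holds is that such a child could receive more, and several times more toward the upper end. Nor does a comparison of milligrams per kilogram between a light and a heavy child add evidence of harm; it only restates that the dose is not scaled.

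Finally, a reader might try to put a frequency on this from section 9.1.8, which lists infusion-related reactions among events in at most 3% of patients. That figure is not specific to Grade 3 or 4 reactions, to children under 20 kg, or to use of the subcutaneous option, so it does not estimate the relevant event.

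**Conclusion.** The point holds as an unscaled dose that is inconsistent within its own row. Below 20 kg, all of the optional 0.2 to 1 mg subcutaneous range exceeds the 0.01 mg/kg that the row prints for the same strength. The 20 kg threshold is exact, and the protocol explicitly provides for patients below it. This rests on reading the range across the page break as 0.2 to 1 mg, which is the natural reading, and on using the intramuscular dose as an internal reference only. There is no arithmetic error in the row.

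Reach is very small. Dose escalation is complete (section 5.1), and Part B plans 8 patients, with 15 at most (section 11.1). An antihistamine is to be given before each infusion. The case for acting is that the edit costs almost nothing and leaves the intramuscular option in place. It is a low-priority safety correction with no bearing on DLT rules, endpoints or sample size.

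**What to change.** In the Grade 3 or 4 row of the section 6.3 table:

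1. Delete the fixed subcutaneous figure, or replace it with a per-kilogram dose and a maximum set by the sponsor's clinical and pharmacy leads.
2. Keep the 0.01 mg/kg intramuscular dose.
3. Have the same leads review the unscaled intravenous range in the same edit, so that the cell is not left partly unscaled. They may also consider whether the intramuscular dose needs a maximum; nothing here shows that it does.
4. State that institutional paediatric anaphylaxis guidelines govern wherever they differ from the row.

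The cost is one table cell at the next amendment. Visits, data collection, DLT definitions, endpoints and sample size do not change.
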